4.4 Information-Motivation-Behavioral Model and Self Efficacy Schema

4.5 Study Measures

4.5.1 Short Physical Performance Battery (SPPB)

At the time of screening patients will undergo a SPPB [APPENDIX F]; patients with a SPPB score of <9 will be allowed to enroll in the study. Patients will complete an SPPB at the completion of the OEP and at 6 months (3 times total). This test will be administered by the Clinical Research Coordinator and scores will be captured. The SPPB is a validated tool composed of a simple battery of objective physical performance tests that involve gait speed, balance and ability to rise from a chair. The SPPB was designed to evaluate balance, gait, strength, and endurance initially in a cohort of 5000 community-dwelling seniors. The tool can be administered in approximately 10 minutes. The SPPB can predict mortality and nursing home admissions among older adults. Interestingly, the measure can also detect a gradient of risk for mortality and nursing home admission among older adults with no current disability.⁹ It also has been shown to predict mortality in cancer survivors.⁵ The tool assesses balance through use of the side-by-side stand, semi-tandem stand, and tandem stand; strength is assessed with the chair stand test and repeated chair stands; and gait speed is evaluated through use of an 8-foot walk test. Scores are assigned for each of the tests and an aggregate score is assigned ranging from 0-12, with higher scores indicating greater physical function. SPPB scores are classified into 4 categories: very low physical function (0-3); low physical function (4-6); moderate physical function (7-9) and high physical function (10-12). An alpha internal consistency of 0.76 has been reported.⁹ The SPPB will be performed twice while the patient is on study, once as a pre-screen enrollment and a second SPPB at completion of the structured exercise program.

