4.5.7 Blessed Orientation-Memory-Concentration Test (BOMC)

The BOMC [APPENDIX L] is a widely used screening test for dementia and evaluation of orientation, registration, and attention. The test allows providers and caregivers to screen for suspected dementia in older patients. It was originally validated on older patients living in both skilled nursing facilities and community-dwelling. The BMOC is a weighted 6-item instrument and takes less than 10 minutes to complete. Scores range from 0-28, and scores greater than 10 are consistent with dementia.

Table 2. Study Measures					
	Study Visit 1: Baseline	Study Visit 2: Completion of OEP*	Study Visit 3: 6 months*		
CARG GA	Х	Х	Х		
SPPB	Х	X	Х		
PROMIS ^a	Х	X	Х		
Falls ^b	Х	X	Х		
OEP Evaluation		X			
Physical Therapy Adherence ^c		Х	Х		
Biomarker ^d	Х	X	Х		
Motivation	Х				
Self-Efficacy	Х	X	Х		
Barriers	Х	X	Х		
Blessed ^e	X*	X*	X*		

*(+/-)30 days; administered monthly; biomarkers (+/-) 14 days

a. PROMIS measures are captured monthly from the time of OEP enrollment (maximum 6 surveys)

b. Falls are captured twice monthly from the time of OEP enrollment via self-report calendar; inpatient falls are captured during hospitalization and are not a self-report.

c. Physical therapy adherence will be captured by the number of visits (inpatient and outpatient) and if patient is achieving the standard based upon the physical therapist assessment (1-achieving the standard, 2-progressing toward the standard, 3-limited progress or not meeting the standard)

d. Blood work will be collected during the study visit with the patients' outpatient hematologist. Attempts will be made to collect blood work during the routine draw, however this is not mandated. Biomarker collection (+/-) 14 days within study visit.

e. If not administered prior to patient's enrollment, the Blessed test will be administered one time at a point after the patient's enrollment in the study.

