6.2 Secondary Endpoint(s)

For the entire cohort of patients, we will describe CARG GA, number of falls, SPPB, PROMIS HRQL scores at all three time points when the relevant data are collected: baseline, after OEP completion and 6 months. Descriptive statistics of these measurements will be provided as well as graphs in order to help visualize the change over time. The proportion of patients who achieve meaningful change in these scores will be described with 95% CI. Difference from baseline will be tested with Wilcoxon signed rank test or McNemar's test for continuous or categorical variables respectively. Take SPPB for example, with 30 patients a two-sided Wilcoxon signed rank test for paired observations will have at least 80% power to detect a medium effect size of 0.55 (i.e. 0.55 standard deviations) for the differences in scores before and after the OEP. Depending on patient retention rate and completeness of the collected data, linear mixed models with repeated measures might be fitted to quantitatively model the changes, but the modeling analysis will mostly be exploratory due to limited sample size. The correlation between these scores including their baseline values and changes over time and other clinical factors of interest such as age, BMI and performance status will also be evaluated.

For patients undergoing transplant, we will describe the following clinical points of interest: inpatient falls, 90-day hospital readmission rate, and length of inpatient stays. Pre and post OEP changes in CARG GA, SPPB and PROMIS HRQL scores and their potential association with these clinical endpoints will be explored graphically.

Findings will largely be exploratory and will need to be validated in larger subsequent multicenter trial.

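### The SPPB score that admits patients also appears to be the baseline for the SPPB change, so that change contains an upward regression-to-the-mean component of unknown size, unless the SPPB in section 3.6 is a separate baseline

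*Combined protocol and SAP*

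**What the plan says.** - **Selection.** Sections 3.1 and 3.2 admit consented patients whose screening SPPB is 9 or below. Section 4.5.1 prints the cut-off as strictly below 9.
- **Number of tests.** Section 4.5.1 says "At the time of screening patients will undergo a SPPB" and "Patients will complete an SPPB at the completion of the OEP and at 6 months (3 times total"). The same section closes with a count of two: the pre-screen and the test at program completion. On either count, the pre-screen is the only SPPB before the Otago program (OEP).
- **Schedule.** In section 4.5.7, "Table 2. Study Measures" marks one SPPB at each of Study Visits 1, 2 and 3 and has no screening column. Table 3 (section 8.0) puts consent and the eligibility check in Study Visit 1.
- **Analysis.** Section 6.2 describes the scores at "all three time points when the relevant data are collected: baseline, after OEP completion and 6 months", then states: "Difference from baseline will be tested with Wilcoxon signed rank test or McNemar's test for continuous or categorical variables respectively". No SPPB comparator is described; the age-matched dataset in section 7.3 is for p16 only.
- **Use.** Section 1.3 lists SPPB change among the measures from which preliminary effect sizes of the exercise program will be calculated.
- **Possible exception.** Section 3.6 names an SPPB as the initial assessment in the paragraph where participants meet the physical therapist. It places Study Visit 1 before the first therapy appointment, although its rule for the 6-month clock allows either order. Nothing says this SPPB is recorded as the analysis baseline.

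Regression to the mean is not mentioned anywhere.

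**The concern.** If the selecting score is also the baseline, the change is biased upward by construction. Some patients pass the cut-off because that day's score fell below their usual level, and on average they return towards it at the next test. The direction needs no normality assumption. For two exchangeable scores, selecting on a low first score cannot lower the expected second score, and it raises it if any patient would cross the cut-off on retest.

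At stake is the SPPB effect size that section 1.3 asks for and that could feed the later multicenter trial mentioned in section 6.2. Without a control group, the data cannot separate this component from an exercise effect.

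**Working it through.** **1. The plan's own figure.** Section 6.2 claims at least 80% power for a two-sided signed-rank test with 30 patients and an effect of 0.55 SD of the differences. Alpha is not stated; I take 0.05. The paired-t noncentrality is 0.55 × √30 = 3.01, giving 82.9%. Multiplying n by the signed-rank efficiency 3/π gives 0.55 × √28.65 = 2.94 and 81.1%; simulation with normal differences gives 80.9%. The figure reproduces. It is, however, power to detect any shift, including one caused by selection.

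**2. Inputs for the bias.**
- From the documents: cut-off 9 or below, range 0 to 12, 30 pairs.
- Assumed: SD 2.5 among screened patients; screened mean 6 to 10; reliability 0.76 to 0.90; mean true change zero; between-patient SD of true change 0 to 2.0.
- The lower reliability comes from section 4.5.1 ("An alpha internal consistency of 0.76 has been reported"). That is internal consistency, so it is only a proxy for test-retest reliability.

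**3. Closed form.** With true score plus independent error and no true change,

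expected rise = (1 − ρ) × SD × φ(c)/Φ(c), with c = (9.5 − mean)/SD.

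- Mean 6, ρ = 0.76: c = 1.4, so 0.24 × 2.5 × 0.1497/0.9192 = 0.10 points.
- Mean 10, ρ = 0.76: c = −0.2, so 0.24 × 2.5 × 0.3910/0.4207 = 0.56 points.
- Mean 10, ρ = 0.90: 0.10 × 2.5 × 0.3910/0.4207 = 0.23 points.

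**4. Simulation.** Scores are rounded and bounded at 0 to 12, with 2,000,000 screened per cell and 6,000 samples of 30 pairs; simulation error is about 1 percentage point. Each cell gives gain in points / two-sided rejection, by between-patient SD of true change.

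| Screened mean | ρ 0.76, SD 0 | ρ 0.76, SD 1.5 | ρ 0.76, SD 2.0 | ρ 0.90, SD 0 | ρ 0.90, SD 1.5 | ρ 0.90, SD 2.0 |
|---|---|---|---|---|---|---|
| 6 | 0.10 / 6.0% | 0.11 / 4.9% | 0.12 / 5.3% | 0.05 / 4.9% | 0.06 / 5.3% | 0.07 / 5.1% |
| 7 | 0.18 / 8.0% | 0.18 / 7.0% | 0.17 / 6.3% | 0.08 / 6.9% | 0.08 / 6.0% | 0.08 / 5.5% |
| 8 | 0.29 / 14.0% | 0.27 / 9.5% | 0.25 / 8.9% | 0.13 / 8.1% | 0.12 / 6.4% | 0.11 / 6.2% |
| 9 | 0.42 / 25.9% | 0.39 / 15.5% | 0.35 / 12.4% | 0.19 / 13.2% | 0.18 / 8.5% | 0.15 / 6.5% |
| 10 | 0.57 / 43.2% | 0.54 / 26.8% | 0.49 / 19.9% | 0.26 / 22.4% | 0.24 / 10.6% | 0.21 / 9.1% |

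With a separate pre-exercise baseline, rejection stays at 4.4% to 5.7% throughout.

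**5. Against the planning effect.** At mean 10, ρ = 0.76 and no true change, the SD of the differences is about 1.67. So 0.57/1.67 = 0.34 SD, and 0.34/0.55 = 62% of the planned effect. At means 9 to 10 the share is 30% to 62% with no true change, 17% to 45% with SD 1.5 and 13% to 36% with SD 2.0. At means 6 to 7 it is about 5% to 19%.

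**6. Sensitivity.**
- A wider grid (SD 2 to 3, retest correlation 0.70 to 0.90, no true change) gives 0.02 to 0.79 points.
- Selecting strictly below 9 makes the gain 1.3 to 1.8 times as large.
- An assumed mean true decline of 0.5 points (SD 1.5) gives a net change from −0.43 (mean 6, ρ 0.90) to +0.06 (mean 10, ρ 0.76).
- The screen-failure share is 8%, 42% and 58% at means 6, 9 and 10. At 42% the gain still runs from 0.15 to 0.42, so this share does not identify the bias.

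**The case against.** **The premise is unsettled.** Section 6.2 says only baseline, Table 2 does not call its Visit 1 SPPB the pre-screen, and section 3.6 describes an SPPB when participants meet the therapist. This stands as a condition on the finding. But both counts in section 4.5.1 leave the pre-screen as the only test before the program. If the 3.6 SPPB is separate, it is a fourth test that Table 2 omits and section 6.2 does not name.

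**The size may be trivial.** This also stands. At screened means of 6 to 7 the effect hardly matters, and the 43% needs low reliability, a mean of 10 and no true change in any patient. Some tabulated gain at nonzero SD of true change also comes from bounding at 0 and 12: with a separate baseline and zero mean true change, the shift was −0.09 points at mean 10 and +0.02 at mean 6 (SD 2.0). The conclusion is unchanged.

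**The plan is already cautious.** Section 6.2 says "Findings will largely be exploratory and will need to be validated in larger subsequent multicenter trial". That lowers the consequence but does not remove the bias, and section 1.3 still speaks of the program's impact.

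**Other influences act on a single-arm change.** Practice effects, completer selection and concurrent treatment all apply, and disease decline may offset the rise. The net direction is therefore unknown, and disclosing regression to the mean alone would not make the change attributable to exercise.

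**Conclusion.** The concern holds. As sections 4.5.1, 6.2 and Table 2 read, the admitting score is the baseline of an uncontrolled change, which then contains an upward selection component. Under the stated assumptions its size runs from negligible to a large part of the 0.55 SD planning effect, and the screened mean, SD and retest reliability that would settle it are not in the documents. If the 3.6 SPPB is a separate pre-exercise baseline, the component disappears under this model provided its error is independent of the screening error. The matter is secondary: it should be corrected, but it does not touch the feasibility endpoint.

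**What to change.** State whether the SPPB in section 3.6 is separate from the screening SPPB, and reconcile the answer with section 4.5.1 and Table 2.

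- **If it is separate and done before the first exercise:** use the screening score for eligibility only, name the 3.6 score as the section 6.2 baseline, and keep the change from screening as a sensitivity analysis. The cost is wording plus capture of a score already described. One drawback: section 4.5.1 says of the SPPB "This test will be administered by the Clinical Research Coordinator and scores will be captured", so the rater may differ between a therapist-scored baseline and follow-up.
- **If it is not separate:** report the screen-failure share, already captured under section 3.1, beside the SPPB change and state that the change includes regression to the mean. Do not label the uncorrected change or its p-value an exercise effect, or carry it unadjusted into planning of the later trial. The cost is wording and one proportion. The component is then disclosed, not removed.
- **Optional:** a reliability-based correction, shown only as a range. At mean 10 its residual error runs from −0.23 (true reliability 0.90, assumed 0.76) to +0.37 (the reverse), against a bias of about 0.26 to 0.57.

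As editorial points, reconcile the strict cut-off in section 4.5.1 with sections 3.1 and 3.2, and the two test counts within section 4.5.1.

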6.3 Correlative Analysis

Presence of deleterious genes and p16 pre-OEP and post-OEP will be correlated with clinical factors (age, performance status, adherence to OEP), GA profiles, SPPB scores.

Serum studies evaluating mRNA will be characterized and analyzed in relation to functional assessment outcomes as well as clinical outcomes of interest. microRNA measures will be assessed in relation to cytokine measures using graphical analyses and measures of correlation. FDR corrections will be utilized to correct for the simultaneous comparisons of the multiple markers.

Quantified p16 expression pre and post OEP will be described, and independently analyzed in relationship to functional assessment outcomes such as GA scales, SPPB Scores as well as

clinical outcomes of interest (age). In addition, p16 expression will be evaluated in relation to clinical outcomes, such as tolerance of OEP, adherence of OEP, length of hospitalization and readmissions in a descriptive manner. Generalized linear models will be used similar to those described above to assess the impact of p16 expression on GA scores depending on data completeness. Spearman rank correlation coefficients will be used in relation to continuous measures (e.g. age), two-sample tests (Wilcoxon rank sum tests) will be used for comparing p16 expression between two groups (e.g. incidence of del17), and Kruskal-Wallis tests will be used to compare p16 expression between more than two groups. Descriptive statistics and graphical analyses will be used to evaluate p16 expression within each of the groups to better understand potential trends of interest.

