Given the serious toll on health status associated with chemotherapy and transplant, the main purpose of this proposal is to conduct a feasibility study to examine predictive measures (SPPB and p16 expression) and preventative measures (OEP) to improve outcomes in patients with hematologic malignancies. Engaging patients in physical activity during therapy is a significant departure from the standard, as patients were previously deemed too ill or too chemotherapy toxic for physical activity intervention. However, with novel therapies and advances in supportive care, our proposed approach to preventing functional decline during transplant is overdue. However, a feasibility study in a single institution is necessary in order to address practical issues in patient recruitment and retention, OEP implementation, and barriers to optimal study delivery and patient safety in this patient population. Here, p16 will be evaluated in the context of a clinical phenotype of fitness, which has not been previously explored. The work accomplished here will inform future multi-study centers to test the effectiveness of the OEP in improving fitness and treatment outcomes (e.g., fall reduction, shorter length of stay during transplant, improvement in quality of life) among hematologic malignancy patients.

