2.3 Molecular biomarkers are associated with aging, frailty, and physical inactivity

Advances in biomarkers of aging can improve upon subjective measures and better quantify physiologic age. Recently, investigators have refined the ability to quantify biologic age by use of a molecular marker, p16. p16 is a tumor suppressor protein that inhibits cell cycle progression, promotes cellular senescence, and has been associated with frailty phenotypes, physical inactivity, and age related comorbidities.¹² p16, originating from the *INK4/ARF* locus on chromosome 9p21, belongs to a family of cyclin-dependent kinase (CDK) cell cycle inhibitors and prevents cell cycle progression by blocking CDK4/6 dependent phosphorylation of the retinoblastoma tumor suppressor (Rb).¹³ Prolonged expression of p16

promotes irreversible cell cycle arrest or cellular senescence. p16 tumor suppressor levels increase exponentially with chronologic aging across most mammalian species including humans.^{14,15} Beyond age, p16-induced senescence can be triggered by variety of internal stressors including DNA damage, replication errors, telomere erosion, and reactive oxygen species.¹⁶ External stressors can also trigger p16 expression such as physical inactivity, chemotherapy, and tobacco exposure. Additionally, single nucleotide polymorphisms located near the INK4/ARF locus are linked with age-related diseases including cardiovascular disease, diabetes and decreased physical function.¹⁷⁻¹⁹ Therefore, it is believed that p16 levels reflect a physiologic age or fitness. Recently Liu and colleagues demonstrated a means of quantifying this molecular marker of age in peripheral blood T-cells,²⁰ providing a feasible and relatively non-invasive strategy to monitor p16 expression over time in a clinical setting to predict treatment tolerance and guide clinical decision making. In this research proposal, we focus on the most validated biomarker (p16) however, we are also exploring immunosenescence of aging (T-cell subpopulations, CD28 expression), markers of energy, and epigenetic markers (DNA methylation, miRs). Additional biomarkers of aging and an immunosenescence panel will be collected and explored.

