2.5 Frailty

Frailty is thought to be highly prevalent among older adults and it confers high risk for including mortality, adverse health outcomes institutionalization, falls. and hospitalization.^{28,29} It is now defined as a biologic syndrome of decreased reserve and resistance to stressors, resulting from cumulative declines across multiple physiologic systems, and causing vulnerability to adverse outcomes. Markers of frailty include ageassociated declines in lean body mass, strength, endurance, balance, walking performance, and low activity.³⁰ Linda Fried, using data from the Cardiovascular Health Study, operationalized a frailty phenotype. She specified that a frailty phenotype was identified by the presence of three or more of the following components: unintentional weight loss of ten or more pounds in the prior year or more than 5% of body weight in the prior year; grip strength in the lowest 20% at baseline, adjusted for gender and body mass index; exhaustion by self-report; slowness, indicated by the slowest 20% of the population, based on time to walk 15 feet, adjusting for gender and standing height; and being among the lowest quintile of physical activity based on a weighted score of kilocalories expended per week. Patients with one or two criteria were considered prefrail. Mortality was six-fold higher for those who met frailty criteria at baseline than that for non-frail for 3-year cumulative survival.³¹

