3.2 Patient Selection Inclusion Criteria

- Patients with hematologic malignancy receiving care (chemotherapy, immunotherapy, targeted agents, bone marrow transplant, or other) for their hematologic malignancy at the Ohio State University.
- Age ≥ 60 years
- Impairments in physical function, as defined by a score ≤ 9 on the SPPB pre-screen
- Medical clearance from an oncologist or primary care physician stating the participant is able to participate in an unsupervised, moderate-intensity physical activity program
- Ability to understand and the willingness to sign a written informed consent document

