7.0 CORRELATIVE ANALYSIS / SPECIAL STUDIES

7.1 Overview

Peripheral blood will be obtained for mRNA, miRNA, and flow cytometry analysis. While specific details of the processing, extraction, and analysis are included in this protocol, these details may change with innovations in laboratory techniques and hence are considered general guidelines only.

7.2 p16 Aging Biomarker: Identifying candidacy for treatment or transplant is generally subjective and is dependent on age, performance status, and comorbidities. The clinical need for objective quantitative measures of physiologic fitness remains unmet. As such, *p16*, a marker of cellular senescence, represents an attractive proxy for physiologic age and may be an additional tool in the clinical evaluation. Many investigations are focusing on biomarkers of age to weigh treatment options and gauge toxicity.⁵⁶ We aim to capture physiologic fitness and with use of *p16* expression in peripheral blood T-lymphocytes (PBTL). The molecular biomarker, *p16^{INK4a} (p16)* is an established marker of systemic cellular senescence associated with physiologic aging. *p16* expression increases ~16-fold over an individual's lifetime and can be readily measured in PBTL.⁵⁷

7.3 Correlative Analysis Procedures: Patients enrolled have peripheral blood collected for p16 analysis serially at three time points 1) pre-OEP 2) post-OEP and 3) 6 months. Peripheral blood will be obtained in EDTA coated tubes (10 ml) where CD3+ T-cells will be isolated using RosetteSep Reagents. RNA will be extracted using RNeasy Plus Mini Kit (Qiagen), and analyzed using reverse-transcription real-time quantitative PCR for p16, ARF, and standard housekeeping genes. p16 mRNA expression will be compared to an age-matched control dataset. The source of this dataset is a primary analysis study previously conducted by the PI, [name] (IRB protocol number 2014C0008). The only information retrieved from this control dataset will be age; no protected health information will be collected. The full dataset has been de-identified and the study team does not have access to identifiable information about this population.

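### The planned p16–SPPB and p16–GA analyses in Section 6.3 do not adjust for age, so they cannot show that p16 adds information on fitness beyond age

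*Combined protocol and SAP*

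**What the plan says.** Section 6.3 (Correlative Analysis) plans to describe p16 before and after the exercise programme and to relate it, one outcome at a time, to functional measures including GA scales and SPPB. The methods named are bivariate. For continuous variables, "Spearman rank correlation coefficients will be used in relation to continuous measures (e.g. age"). Wilcoxon rank-sum tests serve for two groups and Kruskal-Wallis tests for more than two. Age appears in that section only as something p16 is correlated with, never as an adjustment variable.

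One model is mentioned: "Generalized linear models will be used similar to those described above". It concerns the effect of p16 on GA scores, is conditional on data completeness, and lists no covariates. The models described earlier, in Section 6.2, are optional linear mixed models, also without named covariates. SPPB is not included in this p16 model.

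On age, Section 2.3 states that "p16 tumor suppressor levels increase exponentially with chronologic aging across most mammalian species including humans", and Section 7.2 that p16 "expression increases ~16-fold over an individual's lifetime and can be readily measured in PBTL". Section 2.5 gives, as age-associated markers of frailty, "declines in lean body mass, strength, endurance, balance, walking performance, and low activity". Section 2.1 states the aim: "Here, p16 will be evaluated in the context of a clinical phenotype of fitness, which has not been previously explored".

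**The concern.** By the protocol's own account, age raises p16 and lowers the kind of performance that SPPB measures (gait speed, balance and chair rise, Section 4.5.1). Enrolment starts at 60 with no upper limit, so age varies within the cohort. Older patients would then tend to have both higher p16 and lower SPPB even if the two were unrelated among patients of the same age.

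This bears on the question the sponsor wants answered. Section 7.2 says candidacy for treatment already depends on age, among other things, and offers p16 as an additional tool. A correlation that age alone could produce does not show that p16 tells the clinician anything that date of birth does not. Section 7.4 relies on earlier work in healthy volunteers because it reported an effect of lifestyle on p16 independent of age, whereas the present plan does not set that standard for its own p16–fitness analysis.

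**Working it through.** **The plan's own figure.** The only power statement is in Section 6.2: at least 80% for a two-sided Wilcoxon signed rank test of SPPB change with 30 patients and an effect of 0.55 SD. Taking two-sided alpha 0.05 (not stated), a noncentral t calculation with the Wilcoxon efficiency 3/π gives 81.1%, and simulation of the exact test also gives 81.1%. The figure reproduces and this point does not affect it. No power or precision is stated for the p16 analyses.

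**Inputs**
- n = 30, the sample size used in Section 6.2.
- n = 100, the maximum in Section 3.6.
- Age–p16 correlation 0.3 to 0.6 and age–SPPB correlation -0.2 to -0.4. Both ranges are assumptions, because the documents give only the direction of each relation.
- No p16–SPPB relation among patients of the same age (the case of interest).

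**Step 1: correlation induced by age.** With no direct link, r(p16, SPPB) = r(age, p16) × r(age, SPPB).
- Low end: 0.3 × (-0.2) = -0.06.
- High end: 0.6 × (-0.4) = -0.24.

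**Step 2: how often the unadjusted test declares an association.** Use Fisher's z with SE = 1/√(n-3) and d = atanh|r| / SE. The probability is P(Z > 1.96 - d) + P(Z < -1.96 - d).

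| n | SE | r | atanh of absolute r | d | Probability |
|---|---|---|---|---|---|
| 30 | 0.1925 | -0.06 | 0.0601 | 0.312 | 0.0497 + 0.0115 = 6.1% |
| 30 | 0.1925 | -0.24 | 0.2448 | 1.272 | 0.2457 + 0.0006 = 24.6% |
| 100 | 0.1015 | -0.06 | 0.0601 | 0.592 | 0.0856 + 0.0054 = 9.1% |
| 100 | 0.1015 | -0.24 | 0.2448 | 2.411 | 0.6739 + 0.0000 = 67.4% |

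**Step 3: simulation of the Spearman test itself, with and without age.** These were 20,000 normal data sets per case, with p16 and SPPB independent given age. The partial coefficient is (r_PS - r_PA·r_SA) / √[(1 - r_PA²)(1 - r_SA²)], computed on ranks (P = p16, S = SPPB, A = age).

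| Age–p16 / age–SPPB | Unadjusted, n=30 | Unadjusted, n=100 | Partial, n=30 | Partial, n=100 |
|---|---|---|---|---|
| 0.2 / -0.2 | 5.6% | 6.7% | 5.2% | 5.2% |
| 0.3 / -0.3 | 7.6% | 13.9% | 5.2% | 5.0% |
| 0.4 / -0.4 | 12.4% | 32.3% | 4.9% | 5.1% |

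The unadjusted rate rises with the strength of the age correlations and with n. The partial test stays close to 5%.

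**Step 4: does anything else in the plan adjust for age?**
- The model in Section 6.3 covers GA only, is conditional, and names no covariates.
- The age-matched control dataset in Section 7.3 addresses p16 level against controls, not the p16–SPPB association within the cohort.
- Section 6.2 correlates SPPB and the other scores with age as a separate bivariate analysis.
- The false discovery rate correction in Section 6.3 deals with multiplicity, not confounding.

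None of these adjusts the p16–SPPB association.

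**The case against.** The strongest reply is that the marginal association is a legitimate descriptive target. Section 2.1 sets out to compare a biomarker of aging with baseline physical performance, and Section 7.2 calls p16 a proxy for physiologic age. If age links the two, the marginal association is real and Spearman's test detects it correctly. That stands: a reader might take the percentages above as an inflated type I error, but the test is not miscalibrated. What fails is the further inference that p16 informs on fitness beyond age.

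Second, the plan already yields all three pairwise correlations (p16–age, SPPB–age and p16–SPPB), and a first-order partial correlation follows from them. This is true, and it is why the remedy is cheap. But the plan does not say that step will be taken.

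Third, the size may be small. Entry requires age 60 or over and "Impairments in physical function, as defined by a score ≤ 9 on the SPPB pre-screen", which probably weakens both age correlations at baseline, and the 16-fold rise is over a lifetime, not over the enrolled age span. With correlations of 0.2 and -0.2 the effect is negligible. This stands too: 67% is the extreme corner of an assumed range at the maximum sample size, not an expected value.

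Fourth, the stakes are limited. The primary endpoint is programme completion, and Section 6.2 calls the findings largely exploratory and in need of validation. A reader might also infer that the pre/post p16 comparison is confounded by age. It hardly is, since age barely moves within a patient over six months.

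**Conclusion.** The point holds for the cross-sectional p16–SPPB and p16–GA associations. As planned, a positive finding could not be separated from p16 and function both following age. Its size cannot be fixed from the documents. Under the assumed correlations and no direct link, the age-induced p16–SPPB correlation is -0.06 to -0.24, declared significant about 6% to 25% of the time at n=30 and 9% to 67% at n=100. The entry limits make the lower part of these ranges more likely at baseline.

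The documents do not support a claim that any observed p16–SPPB correlation will be spurious, only that the unadjusted analysis could not tell. The feasibility endpoint and the SPPB power statement are untouched. This is a worthwhile, nearly free improvement to an exploratory analysis whose results are meant to inform later multicentre work.

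**What to change.** In Section 6.3:
- Specify the p16–SPPB and p16–GA analyses as partial Spearman correlations controlling for age, or as regressions of the functional score on log p16 and age.
- Name age as a covariate in the p16–GA generalized linear model.
- Report the unadjusted correlations beside the adjusted ones, so that the descriptive aim is kept and the reader sees how much age accounts for.

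The cost is one degree of freedom per analysis and a few lines of SAP wording. Age is already collected, so no new data are needed. Further covariates would use further degrees of freedom and are not required for this point.
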